The novel safety informations were added to section 6.5.1. (Study drug administration). Additional pregnancy β-HCG tests were implemented into section 7 (Visit schedule and assessments) and into the assessment schedule (Table 7-1) and are mandatory for all female patients of child bearing potential at screening, baseline, switch and every study visit.

Changes to specific sections of the protocol are shown in the track changes version of the protocol using strike through red font for deletions and red underlined for insertions.

This amended protocol will be sent to the Institutional Review Board (IRBs)/Independent Ethics Committee (IECs) and Health Authorities for approval. The changes described in this amended protocol require IEC approval prior to implementation.

Protocol Synopsis

Title of study:

A multi-center, randomized, open-label, parallel group study investigating the renal tolerability, efficacy, and safety of a CNI-free regimen (Everolimus and MPA) versus a CNI regimen with Everolimus in heart transplant recipients

Study purpose:

To assess whether a CNI-free regimen with Everolimus and MPA is associated with a better renal outcome as compared to the CNI regimen and Everolimus; while both treatments are expected to be comparable with respect to efficacy.

Objectives:

Primary	
Renal function assessed as glomerula filtration rate (GFR) – MDRD formula – 18 months after heart transplantation
Secondary	
To assess occurrence of treatment failures up to or at Month 18 post Tx, while treatment failure is defined as a composite endpoint of biopsy proven acute rejection of ISHLT 1990 grade \geq 3A (ISHLT 2004 grade \geq 2R), acute rejection episodes associated with hemodynamic compromise, graft loss / re-transplant, death, loss to follow-up (at least one condition must be present)To assess incidence of MACE and each of its components at Month 18 post TxTo assess renal function by GFR – Cockcroft-Gault method – at Month 12 and 18 post TxTo assess renal function (serum creatinine) and evolution of renal function between Month 6 and Month 18 post Tx (creatinine slope)To assess safety and tolerability at Month 6, 9 and 18 post Tx (acc. to safety parameters specified in section 7.6)

Population:

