Since the publication of the results of the 2003 Certican consensus Meeting ([Hummel M, 2005](#)), clinical experience with the use of Everolimus has grown. An increasing number of patients treated outside of clinical studies have provided more information about the efficacy and safety of Everolimus. Based on these recent data, a second Certican Consensus Conference was held in January 2006 ([Rothenburger et al., 2007b](#)). The main goal of the meeting was to discuss new areas for the application and indication of Everolimus in cardiac transplantation. The resulting report summarized the conclusions of the meeting and also brought fourth adaptations and changes in recommendations for the use of Everolimus:

Key Considerations when using Everolimus ([Rothenburger et al., 2007b](#), Table 1)

CNI minimization:

- Maintain target Everolimus trough blood levels 3 – 8 ng/mL
- Monitor Everolimus trough blood levels after changes in dose
- Avoid CYP3A4 inducers or inhibitors where possible
- Statins should be given concomitantly with Everolimus and CsA
- Target CsA C0 trough blood levels of 120 – 150 ng/mL after 3 months and 50 - 100 ng/mL after 6 months

CNI-free:

- Maintain target Everolimus trough blood levels 3 – 8 ng/mL
- Do not eliminate before 6 months post-transplantation
- Closely monitor rejection episodes especially within the first year post-transplantation.

However, further research is needed to address effectiveness of CNI-free immunosuppressive regimen based on Everolimus. The design chosen for the current study follows the abovementioned recommendations. A CNI-free regimen with Everolimus and MPA will be compared with a low-dose CNI regimen and Everolimus. It is expected, that the CNI-free regimen will result in superior renal function, when compared to the CNI-based regimen, while it is expected to be as efficacious and safe as the CNI-based regimen with regard to occurrence of biopsy proven acute rejection episodes, graft loss, and death.

2 Study purpose

This phase IV study is designed to show that an early onset of a CNI-free regimen with MPA and Everolimus in heart transplant patients may be associated with better renal outcome, and similar efficacy as compared to a CNI-based regimen and Everolimus.

3 Objectives

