Unless otherwise stated, all statistical tests will be two-sided and use the 0.05 level of statistical significance. All summary statistics will be presented by treatment group. Frequency distributions will be provided for categorical variables and the two treatment groups will be compared with chi²-tests. Descriptive statistics of mean, standard deviation, minimum, median and maximum will be presented for continuous variables, comparisons of the two treatment groups will be performed with suitable chosen 2-sample tests. Time to event data including rates of affected patients will be assessed by Kaplan-Meier statistics and compared between the two groups with the logrank test.

Data from all centers that participate in this study will be combined.

A detailed description of the statistical evaluation of this study will be provided in a Statistical Analysis Plan which will be finalized prior to closure of the study database.

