10.6 Secondary objectives

10.6.1 Efficacy

The following secondary efficacy variables will be analyzed in an explorative manner:

- Occurrence of treatment failure up to Month 18 defined as composite endpoint of biopsy proven acute rejection of ISHLT 1990 grade \geq 3A resp. ISHLT 2004 grade \geq 2R, acute rejection episodes associated with hemodynamic compromise, graft loss / re-transplant, death, loss to follow up (at least one condition must be present).
- Occurrence of MACE and each of its components at Month 18

Additionally to the analyses of data from the interval between BL (Month 6 post Tx) and Month 18, all secondary outcome criteria will also be evaluated for the interval between Month 0 (prior to Tx) and Month 18.

Event data:

Event rates will be estimated using the Kaplan-Meier method to handle patients who discontinue the treatment prior to suffering from an event adequately. The two groups will be compared using the logrank test.

This procedure will be applied for the composite endpoint of treatment failure and each of its components, as well as MACE and each of its components.

Narratives including relevant medical information will be provided for each biopsy proven acute rejection, CAV, graft loss, or death.

Corresponding data from the NRP group will be described in a similar manner.

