A parallel group design is the most appropriate model to show differences between two treatments. The design includes an initial phase of 3 months during which patients are treated according to center standard outside the trial and an additional 3-months Run in phase with a Cyclosporin A or Tacrolimus based immunosuppressive regimen which is required by clinical needs.

Therapy switch from the CNI-based to the CNI-free regimen after randomization follows experiences from previous clinical trials as well as the recommendations of the second German-Austrian Certican Consensus Conference ([Rothenburger et al., 2007b](#), see [section 1](#) of this protocol).

Blinding of the two study treatments was not reasonable in this trial because dosing of Everolimus,, Tacrolimus and Cyclosporin A has to be based upon trough levels. Therefore the study has to be planned open-label. However, the endpoint of the study is GFR which is an objective outcome variable depending on laboratory measures. An influence of open-label treatment on this primary outcome variable is limited because dosing behavior will mainly be governed by drug trough levels but only in a few expected cases of renal toxicity by the creatinine level.

The randomization visit at Month 6 was scheduled at a time-point after Tx when the adaption of the individual organism to the graft is considered stable, on average of all transplant patients. It is to be expected that the immunological risk at this timepoint is lower, and the benefit of CNI elimination will continue. For this purpose, a CNI-free regimen will be compared with a CNI based immunosuppressive regimen. It is expected, that the CNI-free regimen will result in a superior renal function when compared to the CNI -based regimen, while it is as safe and effective as the CNI-based regimen with regard to occurrence of biopsy proven acute rejection episodes of ISHLT 1990 grade $\geq 3A$ resp. ISHLT 2004 grade $\geq 2R$, acute rejection episodes associated with hemodynamic compromise, graft loss / re-transplant, death, and lost to follow up, as well as of treatment failure (composite endpoint).

A maintenance treatment period of about 9 months under the two regimens, CNI-based versus CNI-free, is considered sufficiently long to explore any differences between both groups in the glomerular filtration rate, which is the primary outcome measure.

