#### **2.6.2      Statistical hypothesis, model, and method of analysis**

Event data:

Event rates were estimated using the Kaplan-Meier method to handle patients who discontinue the treatment prior to suffering from an event adequately. Time to event was defined as the time from date of randomization to the first documented date of the event. The two groups were compared using the log-rank test.

This procedure was applied for the composite endpoint of treatment failure and each of its components, as well as MACE and each of its components.

Narratives including relevant medical information were provided for each biopsy proven acute rejection, graft loss, or death.

Tolerability:

Analyses of renal function as determined by other calculations (serum creatinine, glomerular filtration rate (GFR, Cockcroft-Gault)) were evaluated in the same manner as described for the primary outcome measure.

The creatinine slope (1 / serum creatinine versus time) was determined from all assessments between Month 6 and Month 18 (both visits included) using a linear regression model. These slopes were compared with a two-sided Wilcoxon ranksum test between the treatment groups.

Additionally, tolerability of study medication was assessed from the rate of patients who withdraw prematurely from study medication or in whom study medication had to be converted to another immunosuppressive regimen due to abnormal laboratory results, adverse events, or toxicity. The frequency distribution of these reasons was presented with absolute and percent values. The most frequent reasons (total  $n \geq 5$ ) for discontinuation and/or conversion as well as the total number of patients who are affected by such intolerance of study medication were compared between the two treatment groups using the exact Fisher test.

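### The stated purpose includes showing similar efficacy, but the efficacy plan has only tests of difference and no interval for the difference, so a non-significant log-rank result cannot support similarity

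*Protocol*

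**What the plan says.** **Aim.** Protocol section 2 describes a study designed to show that the CNI-free regimen "may be associated with better renal outcome, and similar efficacy as compared to a CNI-based regimen and Everolimus". The synopsis states the same as an expectation: "while both treatments are expected to be comparable with respect to efficacy". Section 1 ends with a similar expectation for rejection, graft loss and death. Section 11, again introduced as an expectation, says of the CNI-free regimen that "it is as safe and effective as the CNI-based regimen with regard to occurrence of biopsy proven acute rejection episodes", and goes on to name the other components and the composite.

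**Status of the endpoints.** The secondary objective (Protocol section 3, SAP 1.2) is only to assess how often treatment failure occurs. Protocol 10.6.1 adds: "The following secondary efficacy variables will be analyzed in an explorative manner". SAP 2.6.1 says the same.

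**Analysis.** For the composite and each component, Protocol 10.6.1 plans Kaplan-Meier rates, and "The two groups will be compared using the logrank test". SAP 2.6.2 matches: "The two groups were compared using the log-rank test". Protocol 10.1 sets the level: "Unless otherwise stated, all statistical tests will be two-sided and use the 0.05 level of statistical significance". The synopsis and Protocol 10.1 also name generic chi-square or Fisher tests for categorical data.

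**Sizing.** Protocol 10.8 and SAP section 3 size the trial on GFR alone. SAP 1.1 reports 162 patients randomised.

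**The concern.** The renal benefit is worth having only if it is not bought with more rejection, graft loss or death. Protocol section 1 itself lists close monitoring for rejection among the considerations for CNI-free use, so an excess is a recognised possibility.

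A test of no difference can give evidence of a difference. When it does not reject, it says nothing by itself about how large a difference remains possible. The GFR analysis avoids this problem: Protocol 10.5.2 and SAP 2.5.2 require the treatment contrast with its confidence interval. The efficacy analysis has no counterpart, although efficacy is where the stated purpose speaks of similarity and where precision matters most. A report that prints a log-rank p-value above 0.05 next to that purpose invites the reader to take it as confirmation.

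**Working it through.** **1. The plan's own sizing figure.** Inputs from Protocol 10.8: δ = 8 ml/min, σ = 16 ml/min, two-sided α = 0.05, power 90%.

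n per group = 2(1.960 + 1.282)² × 16²/8² = 2 × 10.51 × 4 = 84.1, rounded up to 85. With the noncentral t, power is 90.0% at 85 (just below 0.90 before rounding) and 90.3% at 86. The stated 86 reproduces. It uses no efficacy input, and there is no efficacy figure in either document to reproduce.

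**2. What the log-rank test could detect.** Inputs: 162 randomised (SAP 1.1) with 1:1 allocation, so 81 per arm is assumed; two-sided α = 0.05 (Protocol 10.1); follow-up from randomisation at Month 6 to Month 18 (SAP 2.6.2). Failure probabilities p1 (CNI) and p2 (CNI-free) are assumptions.

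Events D = 81(p1 + p2); HR = ln(1 − p2)/ln(1 − p1); power = Φ(√D × ln(HR)/2 − 1.96).

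| Assumed failure, p1 v p2 | HR | D | √D × ln(HR)/2 − 1.96 | Power |
|---|---|---|---|---|
| 5% v 10% | 2.05 | 12.2 | −0.71 | 24% |
| 10% v 20% | 2.12 | 24.3 | −0.11 | 46% |
| 15% v 25% | 1.77 | 32.4 | −0.33 | 37% |
| 15% v 30% | 2.19 | 36.5 | 0.41 | 66% |
| 20% v 40% | 2.29 | 48.6 | 0.93 | 82% |

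Cross-checks for 10% v 20%: Freedman form 42.4%, two-proportion formula 42.9%, exact enumeration of the chi-square test 42.8%, simulated log-rank (20,000 runs) 42.4%. The Schoenfeld value of 45.6% is the top of that range. At the originally planned 100 per arm, D = 100 × 0.30 = 30 and Schoenfeld power is 53.8%.

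**3. Width of the missing interval.** Half-width = 1.96 × √(2p(1 − p)/81).

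- p = 10% in both arms: 1.96 × √(0.18/81) = 9.2 points.
- p = 20% in both arms: 1.96 × √(0.32/81) = 12.3 points.

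An invented result shows the consequence. With 8/81 (9.9%) v 14/81 (17.3%), the difference is 7.4 points, its standard error is √(0.0988 × 0.9012/81 + 0.1728 × 0.8272/81) = 5.35 points, and the 95% interval is −3.1 to 17.9. It includes zero, yet it is compatible with an excess of nearly 18 points.

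**4. Would a margin have been workable?** The documents name none, so this is only illustrative. For a 10-point margin, one-sided 0.025, with 10% true failure in both arms, power is Φ(0.10/0.0471 − 1.96) = Φ(0.16) = 56%. About 142 per arm would be needed for 80%. At 20% in both arms power falls to 36%. This favours estimating the difference over a formal similarity test added now.

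**The case against.** The case for the plan is that it claims less than section 2 suggests on a quick reading. Section 2 says the regimen may be associated with the outcome, and the synopsis and section 11 state expectations. The operative objective is to assess treatment failure, and the analysis is labelled explorative. An exploratory secondary endpoint does not need a margin or a power statement. The reader will also see more than a p-value, because the plan gives Kaplan-Meier rates by arm for the composite and each component, plus narratives for each biopsy-proven rejection, graft loss and death.

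Most of this stands, and it rules out four stronger readings that a reader might infer:

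- **That the plan intends to conclude similarity from a non-significant log-rank test.** No passage says so. The risk is a misreading that the plan leaves open.
- **That a p-value above 0.05 is the likely result even under a large excess.** This depends on the base rate. Power is about 82% for 20% v 40%, and the documents do not exclude higher rates, since the composite counts loss to follow-up and rejections found on scheduled biopsies.
- **That stopping enrolment early caused the problem.** Power for 10% v 20% would have been about 54% at 200 patients, against 46% at 162.
- **That the log-rank p-value would be the only efficacy evidence.** The rates by arm and the narratives are evidence too.

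The objection does not remove the gap. Rates by arm without an interval for their difference do not show how large an excess remains possible. The generic chi-square and Fisher tests are also tests of difference. Exploratory status makes a similarity conclusion harder to support, while section 2 still names similar efficacy as something the design is meant to show.

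**Conclusion.** The point holds in this form: the stated purpose includes similar efficacy, and the planned between-group analysis cannot support that conclusion when the test is non-significant. The logic does not depend on any event rate.

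The practical size does depend on it. With 81 per arm assumed, power across the assumed scenarios runs from 24% (5% v 10%) to 82% (20% v 40%). The 95% interval for the difference is about ±9 points at 10% failure in both arms and about ±12 points at 20%.

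The documents do not support a charge that similarity is a formal hypothesis or a planned inference. The primary GFR analysis is unaffected. The change is worth making because it bears directly on how the renal result will be weighed.

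**What to change.** In SAP 2.6.2, for treatment failure and for biopsy-proven acute rejection:

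- Add the between-arm difference in Kaplan-Meier failure probability at Month 18 with a two-sided 95% confidence interval, and the hazard ratio with its interval.
- Evaluate the difference at a stated day that includes the Month 18 visit window. SAP 5.1.3 dates rejection by the biopsy, SAP 2.6.2 counts time from randomisation, and Protocol section 7 accepts visits within a week of the planned date. A patient randomised a week early and seen a week late at the end is therefore biopsied two weeks past 12 months. A cut at the nominal day would lose such events. State how completers are censored too, so that the risk set does not empty before that day.
- State that similarity will not be concluded from a non-significant log-rank test, and that efficacy conclusions will quote the upper confidence limit of the difference.

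Record this in SAP section 4. The SAP history dates the document before database lock, so the addition can still be prespecified. In the SAP and the report, treat the similar-efficacy aim as estimating the efficacy difference. Rewording Protocol section 2 is optional, because Appendix 1 requires a written, approved amendment and enrolment is already closed.

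The cost is one more output and a more cautious efficacy conclusion. No margin, extra patients or new data are needed.

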At Month 6 (± 1 week) post transplantation (Baseline), patients whose eligibility is confirmed by additional in- and exclusion criteria will be randomized and hence allocated to one of the two treatment groups in a 1:1 ratio. Patients will then either receive an immunosuppressive regimen consisting of a CNI (Tacrolimus or Cyclosporin A) with Everolimus with corticosteroids or be switched to the CNI-free regimen in the following way:

Starting the day following the Month 6 assessment, Cyclosporin A will be reduced to ≤ 75 ng/mL (according to C0 level) or Tacrolimus will be reduced to ≤ 5 ng/mL (according to C0 level) for 8 weeks and subsequently removed completely. Depending on the initial immunosuppression either MPA or Everolimus will be added to the patient's immunosuppressive regimen. Consequently, patients receive a transitional immunosuppressive regimen of Cyclosporin A or Tacrolimus and Everolimus and MPA or MMF until complete switch to the CNI-free regimen is achieved at 9 months post Tx.

Dose increase / adjustment of MPA should be performed based on the investigator's experience and the given clinical conditions, adverse events, etc. The CNI-free regimen should be achieved after a maximum of 3 months and be stable by Month 9. During the therapy-switch a control assessment will be performed at Month 8.

In all patients, further control assessments will be performed at Month 9, 10, 12 and 18 (end of study and early discontinuation) post Tx.

[figure not shown]
Corticosteroids must be added to the immunosuppressive regimen in all patients, according to local standard. A dose of 0.05 – 0.3 mg/kg prednisolone or equivalent should be continued throughout the whole study.

Obligatory biopsies will be obtained at Month 6, 9, 12, 18. Facultatively biopsies may be obtained at every study visit.

Statistical analysis and report writing will be performed when all patients have completed Month 18 after Tx assessment.

An external and independent Data Safety Monitoring Board (DSMB) will be instituted. The DSMB will review safety-related issues and will be entitled to make recommendations for changes in study conduct. Details on the function of the DSMB will be laid out in a separate DSMB Charter.

Table 4-1 Study outline

Patients should be seen for all visits on the designated day or as close to it as possible.

Baseline visit assessments and randomization (Month 6 post Tx) may be performed within a time window of \pm 1 week.

5 Population

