6.4 Treatment blinding

This is an open-label study.

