7.5 Efficacy

The following efficacy variables will be obtained and recorded:

- **Endomyocardial biopsy – Rejection episodes / graft loss / re-transplant**

Per protocol biopsies will be performed at visits 2, 4, 6 and 7 and results of a biopsy that may have been performed at Month 1 post Tx will be recorded retrospectively. Additionally, a biopsy will be performed in any case of suspected rejection. Biopsies will be read and interpreted by local pathologists according to the ISHLT 1990 and/or 2004 diagnosis criteria ([Stewart et al, 2005](#)). A copy of the pathology report will be collected and filed in the investigator's folder. The results will be recorded on the Endomyocardial Biopsy CRF at respective visit.

All suspected rejection episodes must be recorded on the Endomyocardial Biopsy log / Suspected Rejection CRF, with the date rejection was first suspected, whether anti-rejection therapy was administered, whether the acute rejection was confirmed or with final clinical diagnosis specified, and final clinical outcome.

Biopsy-proven acute rejection

(ISHLT 1990 grade \geq 3A resp. ISHLT 2004 grade \geq 2R)

The occurrence of a biopsy-proven acute rejection is diagnosed from per-protocol biopsies or from biopsies performed for suspected rejection episodes. Per protocol biopsies will be performed at Visits 2, 4, 6 and 7 / 7.1.

In all suspected rejection episodes, a graft core biopsy and an echocardiography will be performed within 48 hours, regardless of the initiation of anti-rejection therapy. The results including date of occurrence of first symptoms will be recorded in the Endomyocardial Biopsy log / Suspected Rejection CRF and will be used for the efficacy analysis.

Rejection episodes will be reported on the Endomyocardial Biopsy log / Suspected Rejection CRF only, and not on the AE CRF. An Endomyocardial Biopsy log / Suspected Rejection CRF will be completed each time a suspected or biopsy-proven acute rejection has occurred. Rejection episodes occurring more than 10 days after the start of the preceding one will be considered as a new rejection episode.

Rejection with hemodynamic compromise

The occurrence of an acute rejection with hemodynamic compromise will be assessed using the Hemodynamic Compromise CRF. Positive inotrope therapy or vasoactive treatment will be recorded on the Prior-/Concomitant medications CRF.

Graft loss / re-transplantation

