#### Biopsy proven acute rejection

- Source : Endomyocardial biopsy CRF at respective visit
- Occurrence: “ISHLT grade / 1990” in (“Grade 3A”, “Grade 3B”, “Grade 4”) AND/OR “ISHLT grade / 2004” in (“Grade 2R moderate”, “Grade 3R severe”)
- Date of event: “Date of biopsy”

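### Facultative biopsies may make rejection surveillance unequal between open-label arms, and the SAP's rule for biopsy-proven rejection has no filter on indication where the protocol's has one

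*Protocol*

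**What the plan says.** - **Schedule.** Protocol section 4: "Obligatory biopsies will be obtained at Month 6, 9, 12, 18", the same in both arms. It then adds: "Facultatively biopsies may be obtained at every study visit". The Synopsis says the same. No rule covers when, why or in which arm a facultative biopsy is taken.
- **Blinding and reading.** Protocol 6.4: "This is an open-label study". Protocol 7.5: "Biopsies will be read and interpreted by local pathologists". No central or blinded reading is stated.
- **Background.** In Protocol section 1, the consensus points for CNI-free use, but not those for CNI minimization, include: "Closely monitor rejection episodes especially within the first year post-transplantation". The section goes on: "The design chosen for the current study follows the abovementioned recommendations".
- **Event definition in the protocol.** Section 7.5: "The occurrence of a biopsy-proven acute rejection is diagnosed from per-protocol biopsies or from biopsies performed for suspected rejection episodes". It places per-protocol biopsies at Visits 2, 4, 6 and 7/7.1.
- **Event definition in the SAP.** Section 5.1.3 names as source the "Endomyocardial biopsy CRF at respective visit", accepts any grade of 3A or higher (1990) or 2R or higher (2004), and dates the event at the biopsy. It does not mention indication.
- **Analysis.** BPAR enters treatment failure. SAP 2.6.2 compares the composite and each component by Kaplan-Meier and log-rank. SAP 2.6.1 calls these analyses exploratory.
- **Not planned.** Neither document has a count of biopsies by arm or an analysis by indication. SAP section 4 lists no change to the BPAR definition.

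**The concern.** A silent rejection is found only if a biopsy is taken while it is present. An investigator who knows the arm decides on the extra biopsies, and they can fall at Months 8 and 10, around the completion of CNI withdrawal at Month 9. If one arm has more of them and their findings count, that arm can show more BPAR and treatment failure, with earlier event dates, even when the true risk is equal.

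Protocol section 11 defends the open-label design by the objectivity of GFR. That argument does not cover an endpoint whose detection depends on a decision to biopsy. The study purpose pairs better renal outcome with similar efficacy, so readers will weigh any renal gain against the rejection comparison.

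**Working it through.** The plan has no figure of its own to reproduce here. Its sample size concerns GFR, and the documents give no rejection rate, margin or power for rejection.

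**Step 1: the two event rules**

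| Biopsy | Protocol 7.5 | SAP 5.1.3 |
|---|---|---|
| Per-protocol (Visits 2, 4, 6, 7/7.1) | counts | counts |
| For suspected rejection | counts | no filter, but these also have a separate log/Suspected Rejection form |
| Facultative, Month 8 or 10, no suspicion | not named | no filter; counts if recorded on the biopsy form |

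The protocol does distinguish by type of biopsy elsewhere: the Month 6 to 9 rejection criterion for withdrawal in 6.5.6 is tied to per-protocol biopsies.

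**Step 2: inputs**

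From the documents: 3 obligatory biopsies after randomization (Months 9, 12, 18); 2 further visits without one (Months 8, 10), so at most 5; 162 randomized 1:1, taken as 162/2 = 81 per arm. All yields, rejection rates and uptakes below are assumptions.

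**Step 3: upper bound.** Every patient in one arm has both extra biopsies and nobody in the other does. Biopsies are independent with the same yield p in both arms. Detected proportion = 1 − (1 − p)^k, with k = 3 against k = 5. The last column is the chance of a two-sided 5% difference between proportions at 81 per arm.

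| p | k = 3 | k = 5 | Difference (points) | Ratio | False significance |
|---|---|---|---|---|---|
| 1% | 3.0% | 4.9% | 1.9 | 1.65 | 9% |
| 2% | 5.9% | 9.6% | 3.7 | 1.63 | 14% |
| 3% | 8.7% | 14.1% | 5.4 | 1.62 | 19% |
| 5% | 14.3% | 22.6% | 8.4 | 1.59 | 28% |

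**Step 4: partial uptake, same logic.** Excess = 2 visits × yield × difference in uptake:

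- 2 × 0.02 × 0.20 = 0.8 points
- 2 × 0.05 × 0.40 = 4 points (0.04 × 81 = 3.2 patients)
- 2 × 0.08 × 0.60 = 9.6 points

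This too is an upper figure. It treats every Month 8 or 10 finding as additional, although the obligatory Month 9 biopsy is one month from each.

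**Step 5: milder model.** Equal true risk in both arms; 0.2 or 0.4 episodes per patient over Months 6 to 18; 25% symptomatic and detected at onset; the rest silent for a mean of 1 or 2 months and detected only if a biopsy falls within that time. Log-rank test, 81 per arm, 1,000 simulated trials per setting, extra biopsies for all patients in one arm only.

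| Episodes | Mean silent duration | Without extra | With extra | Difference (points) | False significance |
|---|---|---|---|---|---|
| 0.2 | 1 month | 8.3% | 9.5% | 1.2 | 5.7% |
| 0.2 | 2 months | 10.5% | 11.7% | 1.1 | 5.6% |
| 0.4 | 1 month | 15.9% | 18.1% | 2.1 | 7.0% |
| 0.4 | 2 months | 20.1% | 22.1% | 2.0 | 6.8% |

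In patients, 0.011 × 81 = 0.9 to 0.021 × 81 = 1.7. With half the patients of one arm biopsied, the differences are 0.8 to 1.4 points. The simulation error of a 5% rate is √(0.05 × 0.95/1000) = 0.7 points, and the settings without extra biopsies gave 3.8% to 5.7%. The false-positive rate is therefore raised slightly at most.

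**Step 6: timing.** A silent episode found at Month 8 instead of 9 is dated 1 month earlier; one found at Month 10 instead of 12 is dated 2 months earlier. The log-rank comparison sees this shift even where the count does not change.

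**The case against.** - **Facultative biopsies may not count at all.** A reader might infer from SAP 5.1.3 that every facultative finding is an event. The documents do not settle this. Protocol 7.5 points the other way, and the SAP source line repeats the protocol's name for the form that carries visit biopsies. Table 7-1 shows no biopsy at Months 8 or 10, and no text says where one taken then is recorded. What stands is an unreconciled difference between the two documents.
- **Unequal use is not shown.** A reader might infer that the extra biopsies will fall mainly on CNI-free patients. That rests on one background bullet, which asks for close monitoring of rejection without mentioning biopsies. The obligatory schedule and the visits are identical, and no passage tells investigators to biopsy one arm more. Unequal uptake remains possible under open-label conduct, and no planned table would reveal it.
- **The endpoint is secondary.** It is exploratory, and the GFR analysis is not directly affected. If CNI-free patients are biopsied more, the bias runs against the experimental regimen and cannot create a false impression of equal efficacy. This holds, and it lowers the priority.
- **Narratives already cover each BPAR.** They give context for each event but do not show how often each arm was biopsied.
- **Facultative findings are real rejections.** This is right. A rule to disregard a difference seen only with them would discard a possible signal around CNI withdrawal.

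**Conclusion.** The point holds as a cheap improvement to the SAP. The BPAR rules in the two documents differ, the difference is not declared in SAP section 4, and unequal surveillance could distort the rejection comparison without being visible in the planned output. The likely size is about 1 to 2 points or less, roughly one or two patients per arm. Only the upper-bound models reach more, up to 8.4 points with full one-sided uptake or 9.6 with the highest assumed yield and uptake difference. All of these sizes rest on assumed rejection rates, yields and uptake. The direction depends on which arm is biopsied more. The documents do not show that surveillance was in fact unequal, that facultative findings were counted, or that the primary conclusion is at risk.

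**What to change.** 1. In SAP 5.1.3, reconcile the BPAR rule with Protocol 7.5 and name every form from which biopsies are taken. List any intended departure in SAP section 4.
2. Classify each biopsy as per-protocol (including Visit 7 at early discontinuation and Visit 7.1), for-cause (linked to a Suspected Rejection entry) or facultative. Protocol 7.5 has that form completed for biopsy-proven rejections too, so the link should require a suspicion that did not arise from the biopsy's own result. Otherwise every positive facultative biopsy would become for-cause.
3. Tabulate the number of biopsies per patient by arm and class.
4. Report BPAR and treatment failure twice: with all biopsies, and with per-protocol plus for-cause biopsies only.
5. Interpret with caution a difference that appears only when facultative biopsies are included, without committing in advance to disregard it.

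Cost: SAP wording, one table and one repeat analysis on collected data, with no extra biopsies. The restricted analysis leaves out a few true silent rejections, and for-cause biopsies keep some open-label discretion. The SAP's history table dates it before database lock; if the database has since been locked, label the restricted analysis as post hoc.
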